4 PATIENT SELECTION

4.1 Eligibility criteria

- 4.1.1 Confirmed diagnosis of CMML using the World Health Organization (WHO) classification (appendix E).
- 4.1.2 Age >18 years at the time of obtaining informed consent.
- 4.1.3 Must be able to adhere to the study visit schedule and other protocol requirements.
- 4.1.4 Subjects must be able to provide adequate BM aspirate and biopsy specimens for histopathological analysis and standard cytogenetic analysis during the screening procedure.
- 4.1.5 An Eastern Cooperative Oncology Group (ECOG) performance status score of 0,1, or 2 is required.
- 4.1.6 Women of childbearing potential must have a negative pregnancy test at time of screening and baseline visits and agree to use two reliable forms of contraception simultaneously or to practice complete abstinence from heterosexual intercourse

- 1) for at least 28 days before starting study drug; 2) while participating in the study; and 3) for at least 28 days after discontinuation from the study. The two methods of reliable contraception must include one highly effective method (i.e. intrauterine device [IUD], hormonal [birth control pills, injections, or implants], tubal ligation, partner's vasectomy) and one additional effective (barrier) method (i.e. latex condom, diaphragm, cervical cap).
- 4.1.7 Must understand and voluntarily sign an informed consent form.
- 4.1.8 Must have a life expectancy of greater than 3 months at time of screening.

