	10. Mutational status in our CMML subjects by sanger sequencing of JAK2, c-												
1	CBL, N-RAS, K-RAS,RUNX-1, TET2, SRSF2, EZH2, ASXL1, and DNMT3a												
	(pretreatment and progression).												
	11. Mutational status of JAK2 tyrosine kinase at time of progression by deep												
	sequencing of JAK2 to include M929I, Y931C, G935R, R938L, I960V, E985K.												
	(pretreatment and at progression)												
F11. 01.000													
Eligibility	Inclusion Criteria:												
Criteria	1. Confirmed diagnosis of CMML using the World Health Organization (WHO)												

- classification (appendix E).
- 2. Age >18 years at the time of obtaining informed consent.
- 3. Must be able to adhere to the study visit schedule and other protocol requirements.
- 4. Subjects must be able to provide adequate BM aspirate and biopsy specimens for histopathological analysis and standard cytogenetic analysis during the screening procedure.
- 5. An Eastern Cooperative Oncology Group (ECOG) performance status score of 0, 1, or 2 is required.
- 6. Women of childbearing potential must agree to use two reliable forms of contraception simultaneously or to practice complete abstinence from heterosexual intercourse 1) for at least 28 days before starting study drug; 2) while participating in the study; and 3) for at least 28 days after discontinuation from the study. The two methods of reliable contraception must include one highly effective method (i.e. intrauterine device [IUD], hormonal [birth control pills, injections, or implants], tubal ligation, partner's vasectomy) and one additional effective (barrier) method (i.e. latex condom, diaphragm, cervical cap).
- 7. Must understand and voluntarily sign an informed consent form.
- 8. Must have a life expectancy of greater than 3 months at time of screening.

Exclusion Criteria:

- 1. Any of the following lab abnormalities:
 - Platelet count of less than 35,000/uL
 - Absolute Neutrophil Count (ANC) less than 250/uL
 - Serum Creatinine > 2.0
 - Serum total bilirubin >1.5x ULN
- 2. Use of cytotoxic chemotherapeutic agents, or experimental agents (agents that are not commercially available) for the treatment of CMML within 28 days of the first day of study drug treatment.
- 3. Prior history of metastatic malignancy in past 2 years

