4.2 Exclusion Criteria

- 4.2.1 Any of the following lab abnormalities:
- 4.2.1.1 Platelet count of less than 35,000/uL
- 4.2.1.2 Absolute Neutrophil Count (ANC) of less than 250 cells/uL
- 4.2.1.3 Serum Creatinine \geq 2.0
- 4.2.1.4 Serum total bilirubin >1.5 x ULN
- 4.2.2 Use of cytotoxic chemotherapeutic agents, or experimental agents (agents that are not commercially available) for the treatment of CMML within 28 days of the first day of study drug treatment.
- 4.2.3 Any serious medical condition or psychiatric illness that will prevent the subject from signing the informed consent form or will place the subject at unacceptable risk if he/she participates in the study.
- 4.2.4 Concurrent use of GM-CSF. G-CSF could be used for the short-term management of neutropenic infection. Stable doses of erythropoietin stimulating agents that were started >8 weeks from first ruxolitinib dose or corticosteroids that were being administered prior to screening are allowed.
- 4.2.5 Uncontrolled current illness including, but not limited to ongoing or active infection, symptomatic congestive heart failure, unstable angina pectoris, cardiac arrhythmia, or psychiatric illness/social situations that would limit compliance with study requirements.
- 4.2.6 History of metastatic malignancy in the preceding 2 years.
- 4.2.7 Pregnant women are excluded from this study because ruxolitinib has not been studied in pregnant subjects. Because there is an unknown but potential risk for

adverse events in nursing infants secondary to treatment of the mother with ruxolitinib, breastfeeding should be discontinued if the mother is treated with ruxolitinib.

4.2.8 Patients who have participated in other interventional (treatment-related) clinical trials within 30 days of enrollment are excluded.

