12.3 Handling and Storage

Investigational product must be dispensed or administered according to procedures described herein. Only subjects enrolled in the study may receive investigational product, in accordance with all applicable regulatory requirements. Only authorized site staff may supply or administer investigational product. All investigational products must be stored in a secure area with access limited to the investigator and authorized site staff and under physical conditions that are consistent with investigational product-specific requirements. The bottles of tablets should be stored at room temperature, 15°C to 30°C (59°F to 86°F). Any unused investigational product will be returned to INCYTE for destruction or destroyed at the institution per institutional policy (if allowable).

13 Study Calendar

All screening evaluations will be performed within 4 weeks prior to the start of ruxolitinib treatment. Subjects must have a bone marrow biopsy and aspirate (including

cytogenetics) performed within 4 weeks prior to the start of treatment. All transfusion and pre-transfusion Hgb or platelet count must be recorded for the 8 weeks prior to initiation of study treatment. Strict adherence to the visit schedule is required. In the event that a visit or test cannot be scheduled on the exact visit day, a window of \pm 7 days is allowable. Bone marrow aspiration and biopsy exams can be done within a 14 day window of the allotted date. Tests (including bone marrow biopsies and aspirates) done within the screening period prior to signing informed consent are allowed for use in this study.

- 13.1 **Baseline Assessment**: within 4 weeks of starting treatment Medical history including:
 - disease characteristics such as first diagnosis of CMML, WHO/FAB subtype, IPSS score, MD Anderson Scoring System (MDASC), prior treatments.
 - ECOG performance status.
 - Concurrent medication review.
 - red blood cell and platelets transfusion past 8 weeks if available.
 - Routine physical examination to include vital signs, height and weight.
 - Bone marrow examination, including cytomorphology, cytogenetic assessment, and flow cytometry analysis.
 - Laboratory assessments:
 - Hematology to include platelet count, hemoglobin, hematocrit, white blood cells
 (WBC) and WBC differential (including: neutrophils, eosinophils, basophils,
 lymphocytes and monocytes), INR, PT, and PTT and reticulocyte count.

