 - Clinical chemistries including BUN/urea, creatinine, sodium, potassium,
 alkaline phosphatase, alanine aminotransferase (ALT), aspartateaminotransferase
 (AST), , total bilirubin, bicarbonate, calcium, chloride, glucose, LDH, total protein,
 albumin.
 - Urine or serum pregnancy test for females of childbearing potential will be performed at Screening or on Day 1, prior to first dose of study medication.
 Symptom Score using the The Myeloproliferative Neoplasms Symptom Assessment
 - Form (MPN-SAF). (see Appendix D)

Review and record any blood and blood supportive care products for the prior 8 weeks.

- 13.2 Treatment Period (weeks 1-16): Ruxolitinib will be administered as a twice daily oral dose for a 4-week treatment cycle. Subjects will have a CBC with leukocyte differential performed weekly; a blood chemistry will be performed weekly for first cycle and then q 2 weeks. A BM aspirate and biopsy with cytogenetic analysis will be performed after cycle 2 and 4 (weeks 8, 16) to assess pathologic response, cytogenetic response and disease progression. For subjects who achieve CR, marrow CR, or PR a confirmation bone marrow aspirate and biopsy should be obtained 4 to 8 weeks after documentation of CR, marrow CR, or PR.
- 13.3 Week 16 End of Treatment: Subjects will complete a response assessment within one week after their last administration of ruxolitinib. Subjects discontinuing study early should complete their end of treatment visit within two weeks after their last dose of investigational product. Physical exam, vital signs, concomitant medication, adverse event reporting, CBC, and blood chemistry and BM aspirate and biopsy with cytogenetic analysis will be performed.
- Continuation Phase: After completing cycle 4 response assessments, responders may continue to receive ruxolitinib and the final week 16 dose in the absence of DLT or disease progression until marketing approval of ruxolitinib for CMML. Bone marrow biopsy and aspirate will be repeated after every 4 cycles (For subjects who achieve CR, marrow CR, or PR a confirmation bone marrow aspirate and biopsy should be obtained 4 to 8 weeks after documentation of CR, marrow CR, or PR). A CBC will be obtained and complete metabolic profile as per standard of care. The off treatment assessment should be done within a week off treatment.
- 13.5 Off Treatment assessment: includes best response achieved, date of first response, date of loss of response, reason for discontinuation.

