- 13.6 **Off study evaluation**: include vital status, date of death/last contact, transformation to AML and the date of transformation to AML if applicable. This evaluation will be updated every 6 month for 2 years.

Study Calendar	Pre- Study	Wk 1	Wk 2	Wk 3	Wk 4	Wk 5	Wk 6	Wk 7	Wk 8	Wk 9	Wk 10	Wk 11	Wk 12	Wk 13	Wk 14	Wk 15	Wk 16	Wk 17	Weeks 18-48 (if response) Monthly visits	Off-Study or continue if responding as per previous weeks
Ruxolitiniba		X	X	X	X	X	X	X	X	X	X	X	X	X	X	X	X	X	X	X
Informed consent	X		1																	
Demographics	X				71											L				
Medical history	X					X				X				X				X	X	X
Physical exam	X					X				X				X				X	X	X
Vital signs	X					X				X				X				X	X	X
Height	X																			X
Weight	X					X				X				X				X	X	
Performance Status	X					X		N.		X				X				X	X	X
Concurrent medication review	X								М											
CBC w/diff,	X	X	X	X	X	X	X	X	X	X	X	X	X	X	X	X	X	X	X	X
Retic Count	X					X				X				X				X		
Serum chemistry ^b	X	X	X	X	X		X		X		X		X		X		X		X	X
INR, PT, and PTT	X							1		7						7				
Adverse event evaluation		X				events v								-						
Bone marrow biopsy/aspirate ^d ***	X			١,					X	•			Ĭ				X			
B-HCG ^c	X				4															
Lab. Correlates	X	X				X				X				X				X		

Prior CMML	X																			
Treatments																				
Transfusion	X					X				X				X				X	X	X
Log																				
Response										X								X	X	X
Assessments															_					
Symptom Score Scale ^f	X	X	X	X	X	X	X	X	X	X	X	X	X	X	X	X	X	X		
Scale ^f																				
Off-treatment																		X	X	X
Assessment/Off																				
-Study Follow-					7															
-Study Follow- up/ CMML Summary Form																				
Summary Form																				

- a. Dose as assigned for cohort in phase 1, dose assigned as MTD in phase 2
- b: Albumin, alkaline phosphatase, total bilirubin, bicarbonate, BUN, calcium, chloride, creatinine, glucose, LDH, potassium, total protein, AST, ALT, sodium, and total bilirubin.
- c: Serum or urine pregnancy test (women of childbearing potential).
- d: in addition to specimen required for pathologic review, and additional aspirate will be collected (goal volume of 30cc)
- e: in addition to specimen required for routine labs, 6 green top vials, 1 red top vial; on week 1, peripheral blood will be collected twice: at time of first dose, and 3 hours after first dose.

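### No section clearly requires a negative pregnancy test on the day of first dose, so ruxolitinib can be started on a test up to 28 days old

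*Combined protocol and SAP*

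**What the plan says.** The timing of the pregnancy test is addressed in several places, and they differ.

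- **Section 4.1.6 (eligibility):** "Women of childbearing potential must have a negative pregnancy test at time of screening and baseline visits". The same criterion requires agreement to two contraceptive methods, or abstinence, "for at least 28 days before starting study drug".
- **Section 13.1 and the synopsis Baseline Assessment:** "Urine or serum pregnancy test for females of childbearing potential will be performed at Screening or on Day 1", before the first dose. One test at either time is enough.
- **Section 13, study calendar:** the B-HCG row, whose footnote c reads "Serum or urine pregnancy test (women of childbearing potential"), appears to carry a mark under Pre-Study and none under Wk 1 or later.
- **Synopsis, inclusion criterion 6:** "Women of childbearing potential must agree to use two reliable forms of contraception simultaneously or to practice complete abstinence from heterosexual intercourse". It mentions no pregnancy test.

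On the windows, section 13 states: "All screening evaluations will be performed within 4 weeks prior to the start of ruxolitinib treatment". Section 13.1 gives its Baseline Assessment the same limit ("within 4 weeks of starting treatment Medical history including"). Section 13 also accepts tests done in the screening period before consent was signed.

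**The concern.** There are two related problems.

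The first is a conflict of wording. The eligibility criterion asks for a test at two named visits, whereas the assessment schedule accepts a test at one of two times. A site that follows section 13.1 or the calendar performs one test and cannot tell whether it has met 4.1.6.

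The second would remain even if the wording were aligned. Nothing makes the Day 1 test compulsory: 4.1.6 does not name Day 1, 13.1 makes it optional, and the calendar does not appear to schedule it.

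Section 4.2.7 explains the exclusion: "Pregnant women are excluded from this study because ruxolitinib has not been studied in pregnant subjects". What is at stake is that a pregnancy which begins after the single test, or is too early to show in it, goes unnoticed when exposure starts. The calendar appears to schedule no later test, while dosing is twice daily for 16 weeks and longer for responders.

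**Working it through.** The plan states no figure for the age of the test, so there is nothing to reproduce. The check sets the texts side by side and then works through the two time windows.

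**Step 1. Screening window.** 4 weeks x 7 = 28 days before first dose (section 13). The Baseline Assessment has the same limit (section 13.1 and synopsis), so it too is 28 days.

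**Step 2. Age of the most recent required test at first dose.**

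| Place | Test required | Age at first dose |
|---|---|---|
| 4.1.6 | screening and baseline | up to 28 days, because the only baseline defined shares the screening window; 0 days only if baseline is read as Day 1 |
| 13.1 and synopsis Baseline Assessment | screening or Day 1 | 0 to 28 days |
| Calendar | Pre-Study | up to 28 days |
| Synopsis inclusion 6 | none | not applicable |

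If the general 7-day scheduling allowance in section 13 also stretched the screening limit, the maximum would be 28 + 7 = 35 days. That is an assumption, since the documents do not say the allowance applies there. I use 28.

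**Step 3. What the contraception rule covers.** Let t be the age of the screening test at first dose, so t is at most 28 days. Let c be the time on contraception at first dose, so c is at least 28 days. Then c is never less than t, and a compliant woman is covered for the whole interval from test to dose. A conception within that interval therefore means contraceptive failure or non-compliance.

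**Step 4. What the rule does not cover.** Suppose conception occurred e days before contraception began. Time since conception is then:

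- at the screening test: (c - t) + e
- on Day 1: c + e

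Take a woman who starts contraception on the day of her screening test. She needs 28 days of contraception and her test may be at most 28 days old, so she can be dosed only on day 28, with c = t = 28. At her screening test, time since conception is (28 - 28) + e = e days, which may be too short for a positive result. On Day 1 it is 28 + e days. She meets 13.1, the calendar and the contraception rule, and can be pregnant at first dose.

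The documents give no detection lag. For any lag shorter than 28 days, a Day 1 test would find this pregnancy.

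**Step 5. With a mandatory Day 1 test before dosing.** The age of the last test is 0 days. Sample size, alpha and power do not change.

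**The case against.** The strongest reply is that 4.1.6 governs. It joins the two visits with an and, and uses the plural, so on an ordinary reading a woman with one test is ineligible. The 28-day figure would then follow only if the looser wording of 13.1 overrides the eligibility criterion. It is true that 4.1.6 read strictly asks for two tests. That does not close the gap, because the only baseline the protocol defines is a work-up that may take place up to 4 weeks before treatment. Both tests could be done well before Day 1. Reading baseline as Day 1 would settle the matter, but no text says so. For the same reason, baseline is not wholly undefined. What is missing is a baseline visit distinct from screening.

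Three further points carry weight:

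- **Contraception.** As Step 3 shows, it spans the whole interval for a compliant woman, so 28 days of test age is not 28 days of unprotected risk. The early-conception route matters mainly when the test falls near the 28-day limit. The residual risk is not estimated here.
- **The calendar.** The table is not fully legible, so the absence of a Week 1 mark is weaker evidence than the text. The conflict between 4.1.6 and 13.1 stands without it.
- **Other provisions and scale.** Section 9.3 stops treatment on pregnancy and section 11.6 requires reporting and outcome follow-up. Enrolment is at most 53, and section 2.1 indicates an older population. These limit consequence and frequency, but none of them tests for pregnancy before the first dose.

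**Conclusion.** The concern holds, with high confidence. The sections conflict, and none clearly requires a test on the day of first dose. A site that follows 13.1 exactly can start ruxolitinib on a single test 0 to 28 days old and so could treat a woman whom 4.2.7 excludes.

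This conclusion assumes that baseline in 4.1.6 means the pre-treatment work-up, the only sense the protocol gives it, and that the 4-week screening limit is applied without extension. The affected group is probably small, though its size is not stated. This is a matter of subject safety and consistency with no effect on the statistical design. The change should be made, but the trial's conclusions do not depend on it.

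**What to change.** Use one wording in four places: section 4.1.6, synopsis inclusion criterion 6, section 13.1 and the synopsis Baseline Assessment. It should say that women of childbearing potential need a negative urine or serum test at screening and a second negative test on Day 1, with the result known before the first dose. Add a Wk 1 mark to the B-HCG row of the calendar. Naming Day 1 also removes the need for a separate baseline visit. The Day 1 test is a recommendation, not something 4.1.6 already states.

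The cost is an amendment to four short texts and one calendar mark, plus at most one extra test per woman concerned. No extra visit is needed: the first dose is given in the clinic (section 6.1) and blood is already drawn twice that day (section 16.1).

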4.2 Exclusion Criteria

- 4.2.1 Any of the following lab abnormalities:
- 4.2.1.1 Platelet count of less than 35,000/uL
- 4.2.1.2 Absolute Neutrophil Count (ANC) of less than 250 cells/uL
- 4.2.1.3 Serum Creatinine \geq 2.0
- 4.2.1.4 Serum total bilirubin >1.5 x ULN
- 4.2.2 Use of cytotoxic chemotherapeutic agents, or experimental agents (agents that are not commercially available) for the treatment of CMML within 28 days of the first day of study drug treatment.
- 4.2.3 Any serious medical condition or psychiatric illness that will prevent the subject from signing the informed consent form or will place the subject at unacceptable risk if he/she participates in the study.
- 4.2.4 Concurrent use of GM-CSF. G-CSF could be used for the short-term management of neutropenic infection. Stable doses of erythropoietin stimulating agents that were started >8 weeks from first ruxolitinib dose or corticosteroids that were being administered prior to screening are allowed.
- 4.2.5 Uncontrolled current illness including, but not limited to ongoing or active infection, symptomatic congestive heart failure, unstable angina pectoris, cardiac arrhythmia, or psychiatric illness/social situations that would limit compliance with study requirements.
- 4.2.6 History of metastatic malignancy in the preceding 2 years.
- 4.2.7 Pregnant women are excluded from this study because ruxolitinib has not been studied in pregnant subjects. Because there is an unknown but potential risk for

adverse events in nursing infants secondary to treatment of the mother with ruxolitinib, breastfeeding should be discontinued if the mother is treated with ruxolitinib.

4.2.8 Patients who have participated in other interventional (treatment-related) clinical trials within 30 days of enrollment are excluded.

4.3 Inclusion of Women and Minorities

Both men and women and members of all races and ethnic groups are eligible for this trial.

5 STUDY DESIGN

This is a phase 1/2, two-stage, sequential cohort dose escalation study. In phase 1, subjects will be allocated to BID doses of 10 mg/d up to 40mg/d. The starting dose will be 10 mg/d (5mg BID). Each cohort will include up to 6 subjects. Once MTD is reached, 10 additional subjects will be treated during the first stage of phase 2 (stage 1) at the MTD. The tiral will be terminated if 1 or fewer respond. If the trial goes on to the second stage, a total of 29 patients will be studied to determine efficacy in phase 2.

6 TREATMENT PLAN

6.1 Ruxolitinib administration

Subjects will not take the morning dose of ruxolitinib at the first regularly scheduled visit. Drug will be administered in the clinic in order to obtain adequate biomarker assessment. On all other days corresponding to study visits, subjects will take the morning dose of study drug prior to the visit, and will note on the subject reminder card the time that medications were taken. Reported adverse events and potential risks are described in Section 11. Appropriate dose modifications for ruxolitinib are described in Section 10. No investigational or commercial agents or therapies other than those described below may be administered with the intent to treat the patient's CMML.

6.1.1 Ruxolitinib will be supplied by INCYTE as tablets that will be self-administered BID orally, with or without food approximately 12 hours apart (morning and night).

6.1.2 The dosage strength is 5 mg/tablet Ruxolitinib phosphate (free base equivalent). Administration instructions will be provided at Study Visits. The administration instructions will state that medication is "For Investigational Use Only". Ruxolitinib 5 mg tablets are packaged as 60 count in high-density polyethylene (HDPE) bottles. The bottles will include labeling "New Drug - Limited by Federal (USA) Law to Investigational Use. The bottles of tablets should be stored at room temperature, 15°C to 30°C (59°F to 86°F). Dose escalation guidelines are detailed below in section 6.5. In phase II of the study, a maximum of 29 subjects will be treated at the MTD identified in phase I.

6.2 **Definition of Dose-Limiting Toxicity**

Dose-limiting toxicity (DLT) is defined as any grade 4 hematologic toxicity and any grade 3 or greater non-hematologic toxicity except nausea that is controlled by antiemetic therapy based on the NCI Common Terminology Criteria for Adverse Events (CTCAE) version 4.0. Criteria for Grade 3 renal toxicity are consistent with prescribing information with respect to renal impairment and safe use of ruxolitinib. Grade 3 metabolic/electrolyte abnormalities that are not clinically significant, and are adequately controlled within 72 hours are not to be considered a DLT. To discern disease specific versus drug specific myelosuppression, Grade 4 thrombocytopenia will be defined as a decrease of $\geq 50\%$ of baseline and a level of $\leq 25,000/\text{uL}$. Grade 4 neutropenia will be defined as a decrease of $\geq 50\%$ of baseline and a level of < 500/uL. Previous clinical trials testing ruxolitinib reported a hematologic nadir of 8 weeks. As such, DLTs during the first and second cycle of therapy, i.e. 8 weeks, will be used for the purpose of deciding the dose for next cohort (see dose escalation schema) but DLTs will continue to be evaluated and reported through all cycles on study. Management and dose modifications associated with the above adverse events are outlined in Section 11.

6.2.1 Dose escalation will proceed according to the following scheme:

Dose Escalation Schedu	ıle

Dose Level	Dose of Ruxolitinib (per day given in equal BID
	doses)
Level 1	10 mg
Level 2	20 mg
Level 3	30 mg
Level 4	40 mg

